2.5.4 Windows for time points

Visit windows based on days relative to the first IMP administration will be used to map the efficacy parameters ([Table 7](#)), selected safety variables ([Table 8](#)) and PK/PD variables ([Table 9](#)) to each scheduled visit. Date of randomization will be used as the reference date for patients not treated. The following rules will be applied:

1. For efficacy parameters, only scheduled measurements will be considered. If a patient has more than one measurement for the same parameter at different dates within the same visit window, the one that is closest to the target date will be used (or the latest in case of tie).
2. Only values from the central laboratory will be considered for laboratory variables.
3. For the same laboratory/vital sign/ECG/PK/PD parameter, if a patient has more than one measurement at different dates within the same visit window, the scheduled measurement that is closest to the target date will be used (or the latest in case of tie). If there is no scheduled measurement within the visit window, the unscheduled measurement that is closest to the target date will be used (or the latest in case of tie).
4. When a patient has more than one measurement on the same laboratory/vital sign/ECG/PK/PD parameter on the same date, then the one with the later/largest sample ID will be used.
5. For procedures planned on Visit 2, if it is done on the same date as the first IMP but the performance time is missing, it will be assigned to the Visit 2 time window.

Table 7 – Time window for efficacy endpoints

Visit Label	Target Day	Pre-BD spirometry	Post-BD spirometry	ACQ-5	AQLQ(S), RQLQ(S)
Baseline	≤1	≤1	≤1	≤1	≤1
Week 1	8	2-11			
Week 2	15	12-18		2-21	2-21
Week 3	22	19-25			
Week 4	29	26-32	2-35	22-35	22-35
Week 5	36	33-39			
Week 6	43	40-46	36-49	36-49	36-49
Week 7	50	47-53			
Week 8	57	54-60	50-63	50-63	50-63
Week 9	64	61-67			
Week 10	71	68-74	64-77	64-77	64-77
Week 11	78	75-81			
Week 12	85	82-112	78-112	78-112	78-112
Week 20	141	113-182	113-182	113-182	113-182
Week 32	225	≥183	≥183	≥183	≥183

Table 8 – Time window for safety endpoints

Visit Label	Target Day	Vital signs ^a	Weight	Height	ECG	Haematology, biochemistry, urinalysis	Heptitis and HIV serology tests, quantiferon gold testing, serum pregnancy test	Urine pregnancy test
Baseline	1	≤1	≤1	≤1	≤1	≤1	≤1	≤1
Week 1	8	2-11						
Week 2	15	12-18						
Week 3	22	19-25						
Week 4	29	26-32			2-56	2-42		2-42
Week 5	36	33-39						
Week 6	43	40-46						
Week 7	50	47-53						
Week 8	57	54-60				43-70		43-70
Week 9	64	61-67						
Week 10	71	68-74						
Week 11	78	75-81						
Week 12	85	82-112	≥2		57-154	71-112		71-154
Week 20	141	113-182				113-182		
Week 32	225	≥183			≥155	≥183		≥155

a Except for weight and height

Table 9 – Time window for PK/PD endpoints

Visit Label	Target Day	Serum SAR440340/dupilumab concentration	Anti-drug anti-body	Blood eosinophil/neutrophil	FeNO	Total IL33, sST2, calcitonin	PARC, eotaxin-3	Total IgE, periostin
Baseline	1	≤1	≤1	≤1	≤1	≤1	≤1	≤1
Week 1	8							
Week 2	15	2-21		2-21	2-21			
Week 3	22							
Week 4	29	22-42		22-35	22-42	2-42	2-42	2-56
Week 5	36							
Week 6	43			36-49				
Week 7	50							
Week 8	57	43-70		50-70	43-70	43-70	43-70	
Week 9	64							
Week 10	71							
Week 11	78							
Week 12	85	71-112	2-154	71-112	71-112	71-112	≥71	≥57
Week 20	141	113-182		113-182	113-182	113-182		
Week 32	225	≥183	≥155	≥183	≥183	≥183		

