2.1.4 Safety endpoints

The safety analysis will be based on the reported adverse events (AEs) and other safety information, such as clinical laboratory data, vital signs, electrocardiogram (ECG), etc.

Observation period

The observation period will be divided into 4 epochs:

- The **screening** epoch is defined as the time from the signed informed consent date up to the first administration of the IMP.
- The **treatment** epoch is defined as the time from the first administration of the IMP to the last administration of the IMP + 14 days.
- The **residual treatment** epoch is defined as the time from the last administration of the IMP + 15 days to the last administration of the IMP + 154 days.

The treatment-emergent adverse event (TEAE) period will include both **treatment** and **residual treatment** epochs.

- The **post-treatment** epoch is defined as the period of time starting the day after the end of the treatment-emergent adverse event period up to the patient's end of study (defined as last protocol-planned visit or the resolution/stabilization of all serious adverse events and adverse events with pre-specified monitoring).

The on-study observation period is defined as the time from start of treatment until the end of the study.

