2.1.4.5 Electrocardiogram variables

Recording of a standard 12-lead ECG will be performed at the clinical site at Visits 1, 6, 14 and 17. At the post-randomization visits, ECGs will be performed prior to investigational product administration. A minimum of 3 complexes in an appropriate lead (lead II) will be averaged to determine the PR-interval, QT/QTc-interval, QRS-complex and heart rate will be measured for each ECG. All ECG recordings will be centrally read by independent experts.

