2.1.5 Pharmacokinetic (PK) variables

Pre-dose serum SAR440340 and dupilumab concentrations at Week 0 (baseline), and trough levels at Weeks 2, 4, 8, and 12 will be collected. Follow-up concentrations will be collected at Weeks 20 and 32.

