2.1.6 Anti-drug antibody (ADA) variables

The ADA variables are ADA status and titer over time.

Serum samples for anti-SAR440340 and anti-dupilumab antibody bioanalysis will be collected at Weeks 0 (baseline), 12 and 32. If ADA assessment at week 12 (or the first post-treatment time point analyzed) is positive, additional measurements may be performed from PK samples collected at Week 4. ADA for each drug will be summarized separately.

Patients who discontinue early from treatment may be asked to return to the clinic to have additional PK/ADA samples collected for up to 20 weeks after treatment discontinuation.

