2.4.5 Analyses of safety data

The summary of safety results will be presented by treatment group.

General common rules

All safety analyses will be performed on the safety population as defined in [Section 2.3.2](#), unless otherwise specified, using the following common rules:

- Safety data in patients who do not belong to the safety population will be listed separately
- The baseline value is defined as the last available value prior to the first dose of the IMP
- The potentially clinically significant abnormality (PCSA) values are defined as abnormal values considered medically important by the Sponsor according to predefined criteria/thresholds based on literature review and defined by the Sponsor for clinical laboratory tests, vital signs, and ECG (PCSA version dated May 2014, see [Appendix A](#))
- PCSA criteria will determine which patients had at least 1 PCSA during the treatment-emergent adverse event period, taking into account all evaluations performed during the treatment-emergent adverse event period, including nonscheduled or repeated evaluations. The number of all such patients will be the numerator for the on-treatment PCSA percentage
- The treatment-emergent PCSA denominator by group for a given parameter will be based on the number of patients assessed for that given parameter in the TEAE period by treatment group on the safety population.
- For quantitative safety parameters based on central laboratory/reading measurements, descriptive statistics will be used to summarize results and change from baseline values by visit and treatment group. Summaries will include the endpoint value. The endpoint value is defined as the value collected at or just prior to the last dose date + 14 days, or at end of treatment visit, whichever comes later. If this value is missing, this endpoint value will be the closest value prior to the last dose intake. The worst value is defined as the nadir and/or the peak post-baseline (up to last administration of IMP) according to the direction (minimum or maximum) of the abnormality as defined in the PCSA list
- The analysis of the safety variables will be essentially descriptive and no systematic testing is planned.

All safety values including unscheduled measurements will be assigned to the appropriate safety analysis visit window defined in [Section 2.5.4](#).

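### SAP 2.5.4 labels PK, PD and by-visit safety samples by days from first dose with no on-treatment condition, so a sample taken off IMP can be reported as Week 12, including as the Week 12 PK trough

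*SAP*

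**What the plan says.** SAP 2.5.4 states: "Visit windows based on days relative to the first IMP administration will be used to map the efficacy parameters". The same sentence extends this to safety variables (Table 8) and PK/PD variables (Table 9, "Time window for PK/PD endpoints"). Among several values in a window, the scheduled one closest to the target day is used. For laboratory, vital sign, ECG, PK and PD values, rule 3 adds: "If there is no scheduled measurement within the visit window, the unscheduled measurement that is closest to the target date will be used". None of the five rules mentions the last dose or the EOT visit.

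The Week 12 window is Days 71-112 for PK, eosinophils/neutrophils, FeNO, IL33, sST2, calcitonin and laboratory tests, Days 82-112 for vital signs, and Days 57-154 for ECG.

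SAP 2.1.5 gives the Week 12 concentration a meaning: "trough levels at Weeks 2, 4, 8, and 12 will be collected". It lists Weeks 20 and 32 separately as follow-up.

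Elsewhere the SAP does use treatment status. The safety endpoint value in 2.4.5 is "the value collected at or just prior to the last dose date + 14 days, or at end of treatment visit, whichever comes later". The treatment epoch in 2.1.4 is "the time from the first administration of the IMP to the last administration of the IMP + 14 days". Table 5 in 2.4.4.2 cuts efficacy data at LOAC, OCS use or EOT. Tables 8 and 9 have no counterpart.

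For early stoppers, SAP 2.1.6 and protocol 10.3.4 also allow patients to be asked back to "have additional PK/ADA samples collected for up to 20 weeks after treatment discontinuation".

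**The concern.** Patients with LOAC must stop IMP, so early stopping is built into the design. Whether their later samples enter a Week 12 summary depends on when V15 takes place, and the protocol does not settle that. Flow chart note a, section 10.1 and section 10.1.2.4.1 date visits from first injection, with V15 on Day 141. The Clinical Trial Summary, flow chart notes d and e, and sections 6.1.2 and 6.1.3 have the individual 20-week period begin at the patient's own EOT. Section 10.3.4 points both ways: it runs follow-up to the scheduled study completion date, but also lets the post-treatment period start before Week 12.

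PK has most at stake. A concentration measured long after the last dose could be averaged into the Week 12 trough (SAP 2.4.6.1) and into the tables of concentration by ADA status at each visit (SAP 2.4.7.2), understating exposure. If follow-up counts from EOT, Week 12 biomarker and laboratory summaries could also mix patients on IMP without ICS/LABA with patients off IMP and back on ICS/LABA. That mix would differ by arm if early LOAC is commoner on placebo.

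**Working it through.** **The plan's windows.** The PK limits are midpoints between target days: (57 + 85)/2 = 71 and (85 + 141)/2 = 113. Week 12 is therefore Days 71-112, as in Table 9.

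**Other rules that might close the gap.** SAP 2.4.6.1 drops a concentration only when an injection or sampling date or time is missing. SAP 2.4.6.2 sets no time limit for PD. SAP 2.4.5 and 2.5.5 bring unscheduled safety values into the by-visit summaries. None of these is an on-treatment condition.

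**If V15 is dated from first injection.** Day 141 lies in the Week 20 window (113-182), so no scheduled V15 sample is mislabelled. After an EOT before Day 71, an optional extra PK sample taken on Days 71-112 would still become the Week 12 value through rule 3.

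**If V15-V17 are dated from EOT.** The planned gaps give V15 = EOT + (141 - 85) = EOT + 56 and V17 = EOT + (225 - 85) = EOT + 140. These offsets are inferred; no section states them.

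- V15 is in Days 71-112 when EOT is on Days 15-56 (15 + 56 = 71; 56 + 56 = 112). For vital signs the range is EOT Days 26-56 (26 + 56 = 82).
- An EOT sample on Days 15-56 is never in 71-112, so the closest-to-target rule cannot displace V15.
- With doses on Days 1, 15, 29, 43, 57 and 71, and only doses before EOT counted, V15 falls 57-70 days after the last dose (EOT Day 44: 100 - 43 = 57; EOT Day 15: 71 - 1 = 70). A completer's Day 85 sample is 85 - 71 = 14 days after.
- ECG is not taken at V15 ("12-lead ECG will be performed at the clinical site at Visits 1, 6, 14 and 17"). V17 enters its Week 12 window only for EOT on Days 2-14 (2 + 140 = 142; 14 + 140 = 154).

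**Size of one mislabelled PK value.** Protocol 4.7 says 20 weeks covers about 5 half-lives of SAR440340, so I assume 28 days. In a one-compartment model, a level is the sum of 2^(-days since dose/28) over the doses given.

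- Completer, Day 85: days since dose 84, 70, 56, 42, 28, 14; sum 2.112.
- EOT Day 15, V15 Day 71: 2^(-70/28) = 0.177; 0.177/2.112 = 8.4%.
- EOT Day 44, V15 Day 100: days since dose 99, 85, 71, 57; sum 0.624; 0.624/2.112 = 29.6%.
- All EOT days 15-56 lie between these, with mean 21%. At 21 days the range is 6-22%; at 35 days, 10-35%.

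The documents give no dupilumab half-life, so I make no such calculation for dupilumab.

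**Illustration for an arm (EOT dating only).** The documents do not give LOAC timing or V15 attendance. I assume 60 patients per arm, LOAC 14% on SAR440340 and 40% on placebo (SAP 1.3), LOAC days uniform from a start day to Day 84, 15% of the rest dropping out evenly over Days 1-84, and all LOAC patients attending V15.

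Share off IMP = V15 values from EOT Days 15-56 / (those + completers + EOT on Days 71-84).

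| LOAC starts | SAR440340, dropouts absent | SAR440340, dropouts attend | Placebo, absent | Placebo, attend |
|---|---|---|---|---|
| Day 8 | 4.6/(4.6+46.7) = 9% | 8.5/(8.5+46.7) = 15% | 13.1/(13.1+35.9) = 27% | 15.8/(15.8+35.9) = 31% |
| Day 43 | 2.8/(2.8+48.0) = 6% | 6.7/(6.7+48.0) = 12% | 8.0/(8.0+39.5) = 17% | 10.7/(10.7+39.5) = 21% |
| Day 57 | 0% | 3.9/(3.9+49.4) = 7% | 0% | 2.7/(2.7+43.5) = 6% |

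The resulting fall in the mean SAR440340 Week 12 trough is 0-7% with dropouts absent and 6-12% with them attending. The placebo columns concern biomarkers and laboratory values only.

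**The case against.** The strongest objection is that the main route rests on an inference. Protocol 10.1.2.4.1 is headed to cover early stoppers too, and it books V15 for Day 141. On that instruction no scheduled sample is misplaced. This stands: the 57-70 day gap exists only if follow-up counts from EOT. The optional-sample route remains, but it has no stated timing or number.

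Protocol 6.2.1, with 140 days of follow-up, is tempting as proof of EOT dating. It is not: the same sentence counts 84 treatment days and 252 in total, so it describes completers.

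It is also fair that LOAC may cluster late, because ICS reaches zero only at Week 8 or 9. An EOT after Day 56 puts V15 after Day 112, outside the Week 12 window; the Day 57 row shows the effect.

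Three stronger readings are not supported:

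- A reader might infer that ADA results change, since V17 can fall in the wide Week 12 ADA window (Days 2-154). The summaries in SAP 2.4.7.1 are baseline and patient-level classifications, and no output is shown to change.
- A reader might extend the point to PARC, eotaxin-3, IgE and periostin because their Week 12 windows are open-ended. SAP 2.1.7 schedules none of them after V14.
- A reader might infer bias in the efficacy results. LOAC does not use these windows, and Table 5 governs the main FEV1 analysis.

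On safety, PCSA incidence uses the TEAE period, and laboratory tests, vital signs and ECG also have last on-treatment summaries. PK and PD have no such backup.

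**Conclusion.** The gap is real. As written, SAP 2.5.4 can label an off-IMP sample as Week 12, and nothing else in the SAP prevents it. How far this matters turns on an unresolved conflict in the protocol.

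With V15-V17 dated from EOT, every patient who stops on Days 15-56 and attends V15 would contribute an off-IMP Week 12 value for PK, eosinophils/neutrophils, FeNO, IL33, sST2, calcitonin and laboratory tests. A SAR440340 concentration would then be about 8-30% of a true Week 12 trough, given the assumed 28-day half-life. With V15 fixed at Day 141, that route contributes nothing.

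The number of patients affected cannot be derived from the documents, so the shares above are scenarios and not estimates. Every affected output is descriptive: the harm is to how exposure, biomarker and by-visit safety results are read, not to a test.

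**What to change.** 1. Reconcile the protocol sections on when early stoppers attend V15-V17: flow chart note a, 10.1 and 10.1.2.4.1 against the Clinical Trial Summary, flow chart notes d and e, 6.1.2 and 6.1.3, with 10.3.4 made consistent. Which timing applies is for the sponsor to decide.
2. In SAP 2.5.4, give Week 2-12 PK trough labels only to samples taken within last dose + 14 days plus the protocol's 3-day visit tolerance (14 + 3 = 17 days). Do not add the later-of-EOT extension that 2.4.5 uses for the safety endpoint, because a late EOT sample is not a trough.
3. Give Week 1-12 PD and by-visit safety labels only to samples taken up to the EOT visit or last dose + 14 days plus tolerance.
4. Apply both conditions to scheduled and unscheduled samples. Show later samples as follow-up by time since last dose.
5. Report the number contributing per arm at each visit. State that Week 12 then describes patients still on treatment, a selection that may differ by arm.

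The cost is a condition in the visit-mapping step, using dates already collected, and one protocol clarification. Some Week 12 PK, PD and by-visit safety tables will hold fewer values. The LOAC and main FEV1 analyses do not change.

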2 puffs of 125/25 mcg (250/50 mcg) BID or  
2 puffs of 250/25 mcg (500/50 mcg) BID

Please note that patients should use the same inhaler type (either DPI or MDI) throughout the study.

Patients who satisfy the inclusion and exclusion criteria will be randomized (1:1:1:1 ratio) to one of the following treatment groups:

- SAR440340 (300 mg) administered as 2 SC injections q2w for 12 weeks and coadministration of dupilumab placebo as 1 SC injection q2w for 12 weeks.
- Dupilumab (300 mg) administered as 1 SC injection q2w for 12 weeks and coadministration of SAR440340 placebo as 2 SC injections q2w for 12 weeks.
- SAR440340 (300 mg) administered as 2 SC injections q2w for 12 weeks and coadministration of dupilumab (300 mg) administered as 1 SC injection q2w for 12 weeks.
- Coadministration of matching placebos for SAR440340 and dupilumab administered as 2 and 1 SC injections, respectively, q2w for 12 weeks.

Visits during the 12-week IMP treatment period will occur every week and will be followed by a 20-week observational follow-up period.

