#### **6.1.2 Early treatment discontinuation (ETD) follow-up**

Patients who discontinue IMP treatment prior to completing the 12-week IMP treatment (due to LOAC or due to early treatment discontinuation [ETD]), will be evaluated as soon as possible at the individual patients' End of Treatment (EOT) Visit, using procedures as planned for the EOT Visit at Week 12 (Visit 14). At their EOT visit, patients will resume their prescreening ICS/LABA background therapy and enter the 20-week safety follow-up period/Post IMP Treatment Period (Visit 15 to Visit 17).

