## **10.1.2 Randomized IMP Treatment Phase – Week 0 to Week 12**

### ***10.1.2.1 Background therapy stabilization phase – Week 0 to Week 3 (Visits 2 to 5)***

The visit schedule should be adhered to within the  $\pm 3$  day visit window allowed during the treatment phase of the study.

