2.4.4.2 Analyses of secondary efficacy endpoints

Main statistical model and adjustment of covariates

Change from baseline in pre- and post-BD FEV1 at Week 12 will be analyzed using a mixed-effect model with repeated measures (MMRM) approach. The analysis model will include change from baseline values up to week 12 as response variable and treatment, gender, baseline height, baseline eosinophil strata, region (pooled countries), background ICS dose level at randomization, visit, treatment-by-visit interaction, baseline value and baseline-by-visit interaction as covariates.

Given the potential effects on FEV1 and the goal to obtain as precise a treatment effect estimate as possible, FEV1 values after a LOAC event or initiation of rescue medication will not be included for primary assessment of the secondary endpoints. Inclusion of change from baseline in FEV1 values in the model will follow the rules in Table 5. Data not included in the analysis according to these rules will be set to missing. No imputation will be made for other missing FEV1 measurements.

Table 5 – Data inclusion rules for analyses of secondary and other efficacy endpoints

If the patient has	Use data up to
LOAC with rescue medication ^a	last value before start of LOAC
LOAC without rescue medication ^b	value collected at EOT
OCS use without LOAC	last value before start of OCS
neither LOAC or OCS	value collected at Week 12/EOT

^a If the patient meets at least one of the following three criteria:
- ≥6 additional reliever puffs of salbutamol/albuterol or levosalbutamol/levalbuterol in a 24 hour period (compared to baseline) on 2 consecutive days
- Increase in ICS ≥4 times the last prescribed ICS dose (or ≥50% of the prescribed ICS dose at V2 if background therapy withdrawal completed)
- Requiring use of systemic (oral and/or parenteral) steroid treatment

^b If the patient meets none of the three criteria listed above and meets one or both of the following:
- A 30% or greater reduction from baseline in morning PEF on 2 consecutive days
- Requiring Hospitalization or emergency room visit

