The repeated measures analysis will be based on the restricted maximum likelihood method assuming an unstructured covariance to model the within-subject errors. A Kenward-Roger approximation will be used for the denominator degree of freedom. Descriptive statistics including number of patients, mean, standard error, and least squares (LS) means will be provided for each treatment group. Difference in LS means and the corresponding two-sided 95% CI and p-value will be provided for each pairwise treatment comparison. Sample SAS code can be found below:

```

proc mixed data=fev1data method=reml;
  class usubjid trt01pn sex cntygr1 eosbgp1n icsgrp avisitn;
  model chg = trt01pn sex hgtbl cntygr1 eosbgp1n icsgrp avisitn
    trt01pn*avisitn base base*avisitn /ddfm=kr residual;
  repeated avisitn / subject=usubjid type=un;
  lsmeans trt01pn*avisitn / pdiff cl;
  ods output LSMeans=LSMeans Diffs=Diffs;
run;

```

If the above model fails to converge, the specification may be changed as follows: 1) use maximum likelihood estimation instead of restricted maximum likelihood method; 2) specify a different covariance structure to reduce the number of unknown parameters to be estimated, the path will be UN→TOEPH→TOEP→AR(1).

Sensitivity analysis

The following sensitivity analyses will be conducted to assess the robustness of the main model:

Analyses using the same MMRM model and estimation methods as specified above:

- *Sensitivity analysis 1:* Inclusion of all FEV1 measurements collected up to EOT for all patients. Missing data will not be imputed.
- *Sensitivity analysis 2: Per protocol analysis*

Exclusion of post-baseline FEV1 measurements in patients (and within time windows) where the patient had a protocol deviation considered to have a potential impact on efficacy, ie, (1) intake of a prohibited medication(s); (2) IMP and/or required background therapy non-compliance; (3) entry criteria violation. Deviations will be medically/clinically reviewed during the study, with final classification made and recorded prior to database lock. Missing data will not be imputed.

Analyses with imputation for missing FEV1:

- *Sensitivity analysis 3: Multiple imputation*

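### SAP 2.5.4 gives an early end-of-treatment value no precedence in its visit window, so some values that sensitivity analysis 1 (FEV1) or Table 5 (FEV1, ACQ-5, AQLQ(S)) would include are dropped

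*SAP*

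**What the plan says.** - **Selection rule (SAP 2.5.4, rule 1).** "For efficacy parameters, only scheduled measurements will be considered". If a patient has several on different dates in one window, "the one that is closest to the target date will be used (or the latest in case of tie". Rule 3 lets laboratory, vital-sign, ECG, PK and PD data fall back on an unscheduled value when the window holds no scheduled one. Rule 1 has no such fallback.
- **Windows (SAP 2.5.4, "Table 7 – Time window for efficacy endpoints").** Pre-bronchodilator (pre-BD) spirometry has 7-day windows from target -3 to target +3, except Week 1 (Days 2-11) and Week 12 (Days 82-112). Post-bronchodilator (post-BD) spirometry, ACQ-5 and AQLQ(S) have 14-day windows from target -7 to target +6 for Weeks 6, 8 and 10, and Days 78-112 for Week 12. Their Week 4 window ends on Day 35.
- **Visit timing.** Protocol 6.1: "Visits during the 12-week IMP treatment period will occur every week". Protocol 10.1.2.1 permits a ±3 day "visit window allowed during the treatment phase of the study".
- **Early EOT visit (Protocol 6.1.2).** Patients who stop IMP early "will be evaluated as soon as possible at the individual patients" EOT visit. No study day is fixed.
- **Main-analysis inclusion (SAP 2.4.4.2, Table 5).** For LOAC without rescue medication, data are used up to the "value collected at EOT". For patients with neither LOAC nor OCS, they are used up to the Week 12/EOT value. The other two rows (LOAC with rescue medication; OCS without LOAC) stop before the event. SAP 2.4.4.4 applies Table 5 to ACQ-5 and AQLQ(S) as well.
- **Sensitivity analysis 1 (SAP 2.4.4.2, FEV1 only).** "Inclusion of all FEV1 measurements collected up to EOT for all patients".

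**The concern.** An early EOT visit is tied to the event, not to the visit grid, yet Table 7 assigns it by day number. Suppose Visit 9 takes place on Day 50 and the patient stops with an EOT visit on Day 53. Both pre-BD FEV1 values fall in Days 47-53, and rule 1 keeps Day 50. The post-BD, ACQ-5 and AQLQ(S) values from that EOT survive, because Visit 9 does not collect them and Day 53 opens into the empty Week 8 window. For those endpoints the loss comes elsewhere: an EOT on Day 49 shares Days 36-49 with an on-time Visit 8 (Day 43) and is dropped.

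The value lost is the last on-treatment one, which the inclusion rules name as the end point of the usable data. Sensitivity analysis 1 differs from the main FEV1 analysis by restoring values that Table 5 removes, chiefly the EOT value after LOAC with rescue medication. Where rule 1 then drops that value, the patient can contribute the same data to both analyses, and the robustness check is partly empty.

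The word scheduled adds a second gap. If an early EOT measurement were read as unscheduled, rule 1 would remove every one of them.

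**Working it through.** The documents give no figure for dropped EOT values, so there is none to reproduce. The inputs are the Table 7 windows, rule 1, the weekly visits with ±3 days, and the SAP 1.3 planning values (placebo LOAC 40%, SAR440340 LOAC 14%, 60 patients per group).

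**Assumption.** EOT visits fall uniformly over Days 30-84 and not on a visit day for that parameter. An EOT value counts as dropped when an earlier visit in the same window is strictly nearer the target; ties go to the later value.

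**Visits exactly on target**

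- *Pre-BD FEV1.* Days 30-84 are 55 days. Seven are target days (36, 43, 50, 57, 64, 71, 78), leaving 55 - 7 = 48. The dropped days are the 3 after each target in Weeks 4 to 11: 8 × 3 = 24. Days 82-84 are safe because the Week 12 window holds no earlier visit. Share: 24/48 = 50%.
- *Post-BD FEV1, ACQ-5, AQLQ(S).* Three target days (43, 57, 71) leave 55 - 3 = 52. The dropped days are 30-35, 44-49, 58-63 and 72-77: 4 × 6 = 24. Share: 24/52 = 46%.

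**Visits varying within ±3 days** (independent, uniform; 200,000 simulated draws)

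| Parameter | On target | ±1 day | ±2 days | ±3 days |
|---|---|---|---|---|
| Pre-BD FEV1 | 50% | 39% | 30% | 22% |
| Post-BD FEV1 | 46% | 42% | 38% | 33% |
| ACQ-5, AQLQ(S) | 46% | 42% | 37% | 34% |

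Under ±3 days, the retained value is on average about 2.4 days older than the dropped EOT value for pre-BD FEV1, and about 4.2 days older for the others.

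**Other settings.** Over Days 2-84 with visits on target, the shares are 33/72 = 46% (pre-BD), 24/79 = 30% (post-BD) and 30/78 = 38% (ACQ-5, AQLQ(S)). If every visit were a full 3 days early, or every visit 3 days late, they would be 0/47 for pre-BD and 12/51 = 24% for the others. The result therefore depends on visit timing as well as EOT timing.

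**Patients in sensitivity analysis 1, pre-BD FEV1, if all EOT visits are off schedule**

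- Placebo LOAC: 0.40 × 60 = 24. Lost: 0.22 × 24 = 5.3 to 0.50 × 24 = 12.
- SAR440340 LOAC: 0.14 × 60 = 8.4. Lost: 0.22 × 8.4 = 1.8 to 0.50 × 8.4 = 4.2.

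No matching count can be made for the main analyses, because the shares of LOAC without rescue medication and of stoppers with neither LOAC nor OCS are not stated.

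**The case against.** **Table 5 is a cut-off, not a promise.** It says how far data may be used, and an MMRM by visit needs one value per window. That is fair: some selection rule is necessary. What is missing is an order between the two rules and any protection for EOT. SAP 2.4.5 gives quantitative safety parameters an explicit endpoint value tied to end of treatment; efficacy has no counterpart. Nor does the argument cover sensitivity analysis 1, which claims all FEV1 values up to EOT.

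**Many EOT visits may coincide with weekly visits.** LOAC is evaluated at each of them, and Protocol 9.2.2.2.1 has the PEF-meter data reviewed at study visits. Protocol 10.3.3 also tells patients to contact the investigator when they feel uncontrolled, so the mix is unknown. This stands as a limit on the size. An EOT on the target day of a visit that collects the parameter loses nothing.

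**A reader might infer that the retained value predates the deterioration, so that placebo looks too good at Week 12 and the drug effect shrinks.** The documents do not support that. The retained value may be only 1 to 3 days older and already within the decline, and some stoppers have no asthma worsening at all. Patients with LOAC also receive standard-of-care treatment and resume ICS/LABA. SAP 1.5 itself gives confounding by such medication as a reason for caution with EOT data. An EOT FEV1 could be higher or lower than the value kept.

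**Conclusion.** The point holds as a conflict between stated rules. Under the assumed uniform, off-schedule EOT timing over Days 30-84, rule 1 drops roughly 22% to 50% of pre-BD FEV1 EOT values and 33% to 46% of post-BD FEV1, ACQ-5 and AQLQ(S) EOT values. The upper ends need visits exactly on target; the lower ends use independent ±3 day variation.

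Two broader readings should be avoided. Sensitivity analysis 1 covers FEV1 only, so ACQ-5 and AQLQ(S) losses do not conflict with it. Table 5 itself already removes the EOT value for LOAC with rescue medication and for OCS use, so in the main analyses the conflict is confined to its other two rows.

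The clearest consequence is for sensitivity analysis 1: about 5 to 12 of 24 expected placebo LOAC pre-BD values could be missing if every such EOT visit is off schedule, and fewer otherwise. The direction and size of any bias in litres are not established. The primary LOAC endpoint and the sample size are unaffected. The correction is worth making before database lock because it is cheap and the secondary endpoint's robustness check depends on it.

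**What to change.** Add to SAP 2.5.4, for efficacy parameters:

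1. An EOT measurement after early treatment discontinuation counts as scheduled.
2. The inclusion rule of the analysis concerned (Table 5, or sensitivity analysis 1) is applied before values are assigned to windows.
3. An early EOT value that is included takes precedence over an earlier value in its own Table 7 window.

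The EOT value should keep its own window. Moving it to the next one when its window is occupied would label a Day 81 pre-BD value (85 - 81 = 4 days before target) or a Day 77 post-BD value (85 - 77 = 8 days) as Week 12, the secondary endpoint visit.

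The cost is a few lines in the SAP and one derivation rule. With EOT precedence, none of the included EOT values is dropped. The downside is that an on-time value a few days earlier is displaced in those patients. Sensitivity analysis 1 should therefore be described as using one value per window with EOT taking precedence, since it still would not hold literally every measurement.
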